12.6 Evaluation and Follow-up of RAEs

All RAEs will be forwarded to an ISM for adjudication and follow-up. The ISM may contact the study coordinator to request additional information from the participant, significant other, or their health care provider and may seek medical records from a physician or care setting if needed to make a determination about relatedness to the study. If the event is potentially related to the study, the ISM will consider whether the event was listed in the protocol and ICF and whether modifications to the protocol and ICF should be considered. To ensure the appropriate classification of events, the study physician and/or PI may also be called on to provide additional information.

The ISM will be responsible for providing follow-up for ongoing reportable events, as follows:

1. The ISM will make a determination about relatedness and expectedness of the event and submit a Reportable Adverse Event Evaluation to the study coordinator.
2. If there are follow-ups to an event (and the event is ongoing), the ISM will complete the RAE Follow-up Form to record any updates and submit to the study coordinator.
3. The ISM will follow up on RAEs until a final status has been determined for the event (e.g., recovered, ended in death, is still present, or status is unknown). Some RAEs may have a status of still present at the conclusion of the study. These are the categories of RAE status:
 - a. 'Resolved' is an event that has ended, with or without residual deficits.
 - b. 'Still present' is an event that is ongoing.
 - c. 'Unknown' should be used when the site is unable to make contact with the participant or proxy or to obtain additional information in any other way.
 - d. 'Died' is for an event that ended in death.
4. Once the event is no longer ongoing and a final status for the event has been determined by the study physician, the ISM will confirm the final status, record the closed date, and sign and date the RAE Final Status Form that will be submitted to the study coordinator.

12.6.1 Action Taken

The PI, in consultation with the study physician and the ISM, will decide whether or not an RAE requires that the participant be removed from the study intervention. The UM-OAIC DSMB will be notified of the recommended course of action by the PI in the routine DSMB report. Actions taken in response to the RAE will fall into one of five categories:

• Study intervention modified	• Study assessment modified
• Study intervention suspended temporarily	• No action taken
• Study intervention stopped permanently	

12.7 Responsibilities

The PI has primary responsibility for the safety of participants as it relates to the study protocol. The study coordinator will be responsible for reviewing RAEs and assuring accurate and timely reporting of RAEs. The study physician will be responsible for reviewing RAEs. ISMs will evaluate and classify RAEs and provide follow-up for events until they are resolved. The UM-OAIC DSMB will be responsible for reviewing monitoring data for evidence of harm attributable to participation in the study.

12.7.1 Study Physician

The study physician will be responsible for being “on call” for study-related emergencies and will be available by telephone for consultation with study personnel during all time periods when participants are engaged in the home-based interventions or at clinical assessment visits. In addition, the study physician will be responsible for reviewing RAEs requiring immediate notification to the UM-OAIC DSMB and NIA. The study physician will assess severity and consider whether participation in the study should change for reasons related to safety. The physician will also make a determination about final status once the event has resolved.

The study physician may delegate responsibilities related to immediate notification to a “covering” physician who has been trained on the protocol.

12.7.2 Independent Safety Monitor (ISM)

Physicians will serve as ISMs to review RAEs on a rotating basis. When a RAE is identified the information will be redacted to conceal PHI and then forwarded to the on-call ISM to make a determination. The ISM will be responsible for:

- reviewing reports of RAEs;
- confirming or refuting classification of the event as an RAE;
- evaluating the expectedness of the RAE;
- making a determination about relatedness of the RAE;
- requesting additional information as needed in order to make a determination;
- providing the study coordinator with follow-up reports for ongoing RAEs as new information becomes available;
- confirming the final status for the event once it has been determined by the study physician; and
- submitting a final status report to the study coordinator.

12.8 Reporting Expected AEs and RAEs to the UM-OAIC DSMB

The UM-OAIC DSMB will review tabulated data on non-serious and expected AEs on a semi-annual basis and monitor for adverse event rates out of proportion to those expected. The PI (or designee) will forward the individual Reportable Adverse Event Record and AE Narrative for each event requiring immediate notification to the UM-OAIC DSMB and NIA as well as a table showing all RAEs to the UM-OAIC DSMB and NIA semi-annually. The UM-OAIC DSMB will review all RAEs that are temporally related to the intervention in aggregate form at its scheduled meetings.

All RAEs that relate to hazards of the study intervention or are cause for urgent concern will be reported to the UM-OAIC DSMB chair, NIA, and the UMB IRB immediately after recognition of their importance. The DSMB chair may conclude that an RAE is of universal and immediate concern. The DSMB chair may also recommend convening the UM-OAIC DSMB to review participant safety based on any individual report or accumulating evidence.

Section 13: Intervention Discontinuation

Certain RAEs may result in a temporary interruption or early discontinuation of the trial assessments and interventions or components of these assessments and interventions. Please refer to the appropriate MOP chapter(s) for specific instructions on stopping criteria during screening, intervention, and follow-up assessments.

After such RAEs occur, a participant may resume the trial intervention when the study physician and the primary care provider (if participant has one) agree that it is appropriate. For mild problems that require temporary cessation of intervention, the PI, in consultation with the study physician and participant, may agree to reintroduce the participant to the study intervention.

At any time, the UM-OAIC DSMB may recommend discontinuation of any component or intervention group of the study for any of the following reasons:

- 1) Compelling evidence from this or any other study of an adverse effect of the study intervention(s) that is sufficient to override any potential benefit of the interventions to the target population.
- 2) Compelling evidence from this or any other study of a significant beneficial effect of the study intervention(s), such that its continued denial to other study group(s) would be unethical.
- 3) A very low probability of addressing the study goals within a feasible time frame.

Section 14: Data Analyses

14.1 Primary Aim

The primary aim is to compare the PUSH Plus Protein study subjects (n=30) to those who received PUSH from CAP (n=105). The primary outcome is the distance walked in six minutes (6MWT). Previous analyses of various physiologic measures in the Baltimore Hip Studies data ("BHS"; data unpublished) have shown a $r>0.80$ within subject correlation of measures across time. Preliminary data from CAP-MP have shown a within subject correlation of $r=0.78$ for initial subjects in usual walking speed (n=13).

14.2 Secondary Objectives

A longitudinal analysis using Generalized Estimating Equations (GEEs) will be employed. A model of the form $Y(t) = a + b_1 X + b_2 t_4 + b_3 X t_4$ will be used where: $Y(t)$ is the dependent variable Y at time t (which is 0 or 4 months post baseline testing); a is the intercept; X is an indicator variable for treatment group (PUSH vs PUSH+ Protein); t_4 is an indicator variable for time at 4 months post baseline testing; $X t_4$ is an interaction term for treatment and time; and b_1 through b_3 are empirically derived regression coefficients. An unstructured covariance matrix, an identity link function, and robust standard errors will be used. The effect of intervention on each mechanistic factor will be assessed by estimating the magnitude of the coefficient b_3 , which is interpreted as mean change in outcome from baseline to 4 months comparing PUSH Plus Protein to PUSH alone. The primary outcome will be the 6-minute walk test (6MWT). Other potential outcomes include: activities of daily living (ADLs), quality of life, lower-extremity physical performance, increase of ≥ 50 meters in distance walked in six minutes, cognitive status, and nutritional status.

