The research is based on the premise that successful community ambulation requires certain factors that are influenced by underlying physical or chemical processes. The key factors include endurance, walking speed, muscle strength, balance, lower extremity function, skeletal integrity, and fracture healing. We believe that physical activity and protein supplementation can impact these factors to improve the ability to walk. We want to gain a better understanding of which factors play a role by performing tests that measure physical function, strength, balance, level of inflammation, bone turnover rate, muscle density, and body composition.

Participant data from this pilot study will be compared to data from participants who received the PUSH intervention without protein in two recently completed studies: 1) Community Ambulation Project (CAP parent study) and 2) Community Ambulation Project- Mechanistic Pathways (CAP-MP ancillary study).

Study Title

PUSH Plus Protein Pilot Study for Hip Fracture Patients (hereafter referred to as PUSH Plus Protein)

Objectives

The primary outcome will be to test whether the PUSH Plus Protein intervention improves community ambulation (as measured by distance walked in six minutes) compared to PUSH intervention alone (from CAP study) at the end of 16 weeks. The effects of PUSH Plus Protein on precursors to community ambulation compared to the PUSH intervention alone (CAP study) and the effects of PUSH Plus Protein intervention on the mechanistic factors compared to PUSH intervention alone (from CAP-MP study) will also be examined. In addition, the safety and tolerability of delivering the PUSH Plus Protein intervention to hip fracture patients will be assessed.

Design and Outcomes

In addition to providing important information on adherence, feasibility, and safety, this pilot study of 30 hip fracture patients has the unique advantage of being able to compare data to two recently completed studies where participants received the PUSH intervention without protein supplementation described below.

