Participants in this pilot will receive the same specific multi-component 16-week intervention, PUSH, as participants in the multi-site CAP randomized controlled trial. The PUSH intervention uses a novel machine to provide strength and endurance training in the home. The purpose of this pilot study is to test whether adding a protein supplement to the PUSH intervention leads to greater improvement in a person's functional ability compared to the PUSH intervention alone; therefore, data in this pilot study will be compared to data from participants in the CAP study across the three clinical sites who received the PUSH intervention alone (n=105). Our working hypothesis is that PUSH Plus Protein will lead to greater improvements in ability to walk in the community compared to PUSH measured using the distance walked in six minutes (SMWT).

We will also compare the effect of PUSH Plus Protein intervention to PUSH intervention alone on secondary outcomes in the CAP study believed to be precursors to community ambulation including activities of daily living (ADLs), quality of life, lower extremity physical performance, increase of ≥ 50 meters in distance walked in six minutes, cognitive status, and nutritional status.

We can also compare participants in the pilot study to participants who received PUSH alone in the CAP-MP study (HP-53145) (n=19) to examine whether PUSH Plus Protein has an impact on the mechanistic factors on the pathway to recovery of ambulatory ability after hip fracture. We will assess whether, at the end of the 16 week intervention, participants in the PUSH Plus Protein intervention, compared to PUSH alone, have: a) greater muscle volume and attenuation (i.e., reduced intra-muscular fat) of the thigh; b) greater lower extremity strength; c) better gait parameters; d) greater bone mineral density and bone strength; e) more bone formation and less bone resorption; and f) lower levels of circulating inflammatory cytokines.

The pilot study will provide important information related to the safety and tolerability of delivering the PUSH Plus Protein intervention to hip fracture patients. We will also be able to estimate the sample size requirements for a more definitive study.

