The target sample size for this pilot study is 30 hip fracture patients who will receive the PUSH Plus Protein intervention. Study inclusion criteria are: 1) Closed, non-pathologic, minimal trauma hip fracture with surgical fixation; 2) Age 60 or older at time of baseline testing; 3) Living in the community at time of fracture and at time of baseline testing; and 4) Ambulating without human assistance during the two months prior to fracture. Participants for whom it is not safe to participate in the intervention will be excluded, as will those who are very unlikely to benefit and in whom the intervention is not feasible.

Section 2: Clinical Site

University of Maryland Baltimore
[name]
Principal Investigator
[name]
[name]
[contact]
[contact]
[contact]

Section 3: Study Organization

The PUSH Plus Protein Pilot study is a single-site study conducted at the University of Maryland Baltimore. In addition to the Department of Epidemiology and Public Health (EPH) where the PI has a faculty appointment, the project will utilize resources provided by the Department of Physical Therapy and Rehabilitation Science (PTRS), University of Maryland General Clinical Research Center (GCRC), University of Maryland Investigational Drug Service (IDS), Baltimore Veteran's Affairs Maryland Health Care System (VAMHCS), and the University of Maryland Claude D. Pepper Older American Independence Center (UM-OAIC) Data and Safety Monitoring Board (DSMB). Please see Section 18: for a complete Study Team Roster.

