6.1 Overview of Study Design

A pilot study including 30 older adults who have experienced a hip fracture will be carried out with participants receiving a specific multi-component intervention with protein supplementation (PUSH Plus Protein). Study activities for participants meeting eligibility criteria will take place after post-acute rehabilitation ends, up to 26 weeks after admission to the hospital for hip fracture. Patients age 60 and older who have had surgical repair for hip fracture will be identified in study hospitals or by self-referral and evaluated for eligibility. Following consent to participate, eligible participants will undergo a comprehensive baseline assessment. Participants completing the baseline assessment will be eligible to receive the intervention. All participants will receive the PUSH Plus Protein intervention. The follow-up assessment will occur after the intervention is completed, approximately 16 weeks after baseline testing. Figure 1 shows the sequence of participant contacts from the time of hospitalization until the 16-week assessment.

Figure 1. Timeline for screening and follow-up

Within a week of complete baseline testing, the physical therapist (PT) will initiate the exercise intervention and the protein supplement in the home setting. Participants will also receive counseling with a registered dietitian. The follow-up assessment will take place 16 weeks after baseline testing. Telephone interviews will be conducted every four weeks, beginning four weeks after baseline testing, to obtain information about RAEs and expected AEs, and to help reduce loss to follow-up by maintaining ongoing rapport with participants. An honorarium will be given at the completion of both study assessment visits.

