## **Secondary Objectives**

A longitudinal analysis using Generalized Estimating Equations (GEEs) will be employed. A model of the form  $Y(t) = a + b_1 X + b_2 t_4 + b_3 X t_4$  will be used where:  $Y(t)$  is the dependent variable  $Y$  at time  $t$  (which is 0 or 4 months post baseline testing);  $a$  is the intercept;  $X$  is an indicator variable for treatment group (PUSH vs PUSH+ Protein);  $t_4$  is an indicator variable for time at 4 months post baseline testing;  $X t_4$  is an interaction term for treatment and time; and  $b_1$  through  $b_3$  are empirically derived regression coefficients. An unstructured covariance matrix, an identity link function, and robust standard errors will be used. The effect of intervention on each mechanistic factor will be assessed by estimating the magnitude of the coefficient  $b_3$ , which is interpreted as mean change in outcome from baseline to 4 months comparing PUSH Plus Protein to PUSH alone. The primary outcome will be the 6-minute walk test (6MWT). Other potential outcomes include: activities of daily living (ADLs), quality of life, lower-extremity physical performance, increase of  $\geq 50$  meters in distance walked in six minutes, cognitive status, and nutritional status.

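### The primary comparison is with historical CAP controls, and the planned model does not adjust for cohort differences that affect 16-week change, so b3 cannot be read as the effect of protein

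*Protocol*

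**What the plan says.** Protocol 14.1 states: "The primary aim is to compare the PUSH Plus Protein study subjects (n=30) to those who received PUSH from CAP (n=105"). Section 1 (Executive Summary) describes the controls as "participants who received the PUSH intervention without protein in two recently completed studies", and its Design and Outcomes part adds that they are "data from participants in the CAP study across the three clinical sites who received the PUSH intervention alone (n=105"). Section 3 says: "The PUSH Plus Protein Pilot study is a single-site study conducted at the University of Maryland Baltimore". Section 6.1 says: "All participants will receive the PUSH Plus Protein intervention". The pilot therefore has no concurrent control and no allocation step.

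Section 14.1 gives no model. The only one is in 14.2, repeated in the SAP under Secondary Objectives: Y(t) = a + b1·X + b2·t4 + b3·X·t4, fitted by GEE, with the 6MWT named as primary outcome. X "is an indicator variable for treatment group (PUSH vs PUSH+ Protein"). The SAP says of b3: "which is interpreted as mean change in outcome from baseline to 4 months comparing PUSH Plus Protein to PUSH alone".

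The weight defined in 14.3 (SAP, Missing Data) is the inverse probability of being observed at follow-up. Marginal structural modelling is mentioned as something this weighting can be combined with, but no treatment weight or covariates are given. Protocol 9.5 and 9.5.1 collect background characteristics for description, effect modification and interpretation; adjustment is not among the stated uses.

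**The concern.** CAP's randomisation balanced arms within CAP. It does nothing to make the pilot comparable with CAP. X separates protein from no protein, but equally one site from three, a later period from an earlier one, and people selected for the pilot from people selected for CAP. If any of these affects how far walking distance changes over 16 weeks, the difference appears in b3 with the same standing as a protein effect.

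Followed as written, b3 and its p-value answer whether the pilot cohort changed more than the CAP cohort, yet they are reported as the effect of adding protein. Confounding could create or hide an effect. The pilot is also meant to inform the sample size of a definitive study (Section 1, Design and Outcomes), and a confounded b3 would distort that if used.

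**Working it through.** **Inputs** (Protocol 14.4; SAP, Sample Size Adequacy): effective n of 94 and 27, within-subject correlation 0.70, SD 55.8 (taken as metres; no unit is printed), two-sided alpha 0.05, power 80%.

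**1. Reproduce the plan's figure.**
- SD of change = sqrt(2 × (1 − 0.70)) = 0.775 SD.
- Detectable difference = (1.960 + 0.842) × 0.775 × sqrt(1/94 + 1/27) = 0.474 SD.

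The plan states 0.475, so the planned test is a comparison of changes, and its power assumes that b3 is unbiased. In metres, 0.474 × 55.8 = 26.4. The plan prints 22.9; that mismatch is a separate matter and is not used here.

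**2. Standard error of b3.** 55.8 × 0.775 = 43.2 m; 43.2 × sqrt(1/94 + 1/27) = 9.44 m.

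**3. What the model removes and what it passes on.** In a simulation with no protein effect (4,000 runs per scenario), a stable 20 m gap between cohorts gave a mean b3 of 0.0 m and 5.4% rejections. A 10 m non-protein difference in change gave a mean b3 of 10.0 m and about 20% rejections.

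**4. Sensitivity to an assumed bias B, with no protein effect.** P(reject) = Φ(B/9.44 − 1.96) + Φ(−B/9.44 − 1.96).

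| Assumed B (m) | Two-sided rejection |
|---|---|
| 0 | 5% |
| 5 | 8.3% |
| 6.2 | 10% |
| 10 | 18.5% |
| 10.5 | 20% |
| 15 | 35.6% |

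6.2 m is 6.2/55.8 = 0.11 SD. In the other direction, with a true effect of 26.5 m, a bias of −10 m cuts power from 80% to 42%. Every B is an assumption; the documents supply none.

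**5. Adjusting for baseline 6MWT.** Suppose the cohorts differ by D at baseline.
- If the gap is stable, conditioning on baseline adds about D × (1 − 0.70) to b3. For an assumed D of 20 m that is 6 m (5.9 m in simulation, by weighting or ANCOVA).
- If the gap regresses to the mean, omitting baseline leaves about the same bias with opposite sign (−5.9 m in simulation).

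Neither choice is safe by default.

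**6. Whether weighting can help.** In a simulation (10,000 runs) with a measured confounder assumed 0.5 SD apart and worth 20 m per SD, the unweighted b3 was 10.1 m with 21.0% rejections. A three-covariate overlap weight gave 0.1 m and 3.4%. This is a best case: the confounder is fully measured and the missingness weight is omitted.

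**7. Cost in precision.** Keeping 90%, 70% or 50% of the controls' effective sample gives a detectable difference of 26.8, 27.7 or 29.2 m. Weighting also reduces the pilot's effective sample. With about 24 of 27 and 57 of 94 kept (a confounder assumed 1.0 SD apart), 2.80 × 43.2 × sqrt(1/24 + 1/57) is about 29 m.

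**The case against.** **The plan does handle some confounding.** This stands in part. A reader might infer that nothing at all is controlled, but b3 is a difference in changes, so a stable gap in walking distance falls into b1 and does no harm. What is uncontrolled is any cohort difference that affects change.

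**Imbalance would be visible.** This also stands in part. The characteristics in 9.5 could be tabulated for both studies where CAP holds them, and b1 estimates the baseline 6MWT gap. Seeing an imbalance does not remove it from b3.

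**The studies were made comparable.** The pilot delivers "the same specific multi-component 16-week intervention, PUSH, as participants in the multi-site CAP randomized controlled trial", and 7.1.1 requires certain baseline components so that comparison is possible. These standardise treatment and measurement. They do not address case mix, site or era.

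**Marginal structural modelling is mentioned in 14.3.** Naming a compatible method without an exposure model, weight or covariates is not a plan to use it.

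**It is only a pilot.** Feasibility, adherence and safety do not depend on b3, which limits the consequence. But the protocol states a comparative hypothesis (Section 1 and 4.1) and claims 80% power for it (14.4).

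Some stronger readings should be resisted:
- *That b3 is biased.* CAP's eligibility criteria and entry window are not in the documents, so it is unknown whether the whey-related exclusions (7.3, items 7.1-7.7) or time since fracture separate the cohorts.
- *That the 154 m and 184 m averages in 5.1 size the gap.* They come from other Baltimore work and an earlier pilot at six months post-fracture, not from these two cohorts at entry.
- *That the recovery plateaus cited in 5.1 and 5.2 settle whether time since fracture matters.* Entry at any point up to 26 weeks, with CAP's window unknown, leaves that open either way.

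**Conclusion.** The concern holds and should be fixed before the comparison is analysed. The group indicator is the cohort indicator, the stated model passes cohort differences in 16-week change straight into b3, and no adjustment for them is specified although b3 is read as the intervention effect. This rests on the text of 14.1-14.3 and the matching SAP sections.

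The size of the vulnerability rests on the plan's own n, SD and correlation: about 6 m of non-protein difference is enough to double the nominal error. The existence, size and direction of any bias are not shown. Site, era, case mix and pilot-specific selection are possible sources by inference only. Nor would adjustment make b3 a clean protein effect, because weighting cannot separate protein from calendar period or from unmeasured differences.

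**What to change.** **1. One lead adjusted analysis.** In 14.1/14.2 and the SAP, pre-specify a single confounder-adjusted 6MWT analysis, reported beside the unadjusted b3. Use the same GEE with a propensity weight (for example overlap) for pilot versus CAP, multiplied by the missingness weight. Keep the covariates to a short list of baseline variables recorded in both studies, such as age, sex and MNA-SF, adding the comorbidity index and weeks from admission only if CAP has them. State in advance whether baseline 6MWT is in the lead weight, and report the other version as a labelled sensitivity analysis. If the two disagree, say that the result depends on whether a baseline gap is stable or regresses. Report balance and effective sample size in both cohorts.

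**2. Labelled sensitivity analyses.** Apply exclusions 7.1-7.7 to the CAP and CAP-MP controls where recorded. If the pilot's site contributed CAP PUSH participants, add a same-site comparison.

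**3. Wording.** Remove the references to randomisation of pilot participants, to time post randomisation and to ITT (14.3, 14.4 and the SAP). They do not fit a single-arm study, though they do not affect b3. Describe b3, adjusted or not, as a non-randomised comparison with historical controls in which era effects and unmeasured confounding remain.

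**Cost.** Text and modest programming, with no new pilot data.
- The detectable difference rises from 26.4 m to about 27-29 m, depending on the effective sample kept in both cohorts.
- Weights may be unstable: with 27-30 pilot participants, three covariates leave 9-10 per covariate and five leave 5.4-6.
- A same-site analysis would detect only about 29-36 m if that site supplied 50-20% of the controls (an assumption).
- Everything depends on what CAP recorded. The documents show that it held SPPB, 3MS and nutritional status; they do not show the comorbidity index or weeks from admission.

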14.4 Sample Size Adequacy

Power analyses were conducted for detectable mean changes from baseline (conservatively) assuming a within subject correlation of $r=0.70$. For between group differences, assuming 10% loss to follow up from all causes (mortality, attrition, etc.) by 16 weeks post randomization (CAP n=105 in the PUSH arm and this study will have n=30, so effective n=94 compared to n=27 including attrition). The study will have 80% power to detect differences of 0.475 standard deviations assuming two-sided tests and an alpha level of 0.05. These differences are considered small-to-moderate effects using Cohen's criteria for interpretation of effect sizes (where 0.2 is "small" and 0.5 is "medium"). Given a 6MWT mean of 186.7 and SD=55.8 in the most recent overall sample from CAP (n=199, DSMB report May 2017), this would translate into a difference of 22.9. Similar magnitude of effects (SD=0.41) are detectable comparing to other measures available in the CAP study (e.g, SPPB, 3MS, etc.).

For outcomes only available in the CAP-MP study, the comparison sample is 19 subjects in CAP-MP PUSH. Assuming 10% loss to follow up (n=17 in CAP-MP PUSH group vs n=27 in pilot study), the study will have 80% power to detect between group differences of 0.62 standard deviations assuming two-sided tests and an alpha level of 0.05. This is considered a moderate-to-large effect size by Cohen.

Section 15: Data Capture, Data Management, and Quality Assurance

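### The plan names no small-sample correction or reference distribution for the GEE robust standard errors, although the smaller groups have only 17 to 27 evaluable participants

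*Protocol*

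**What the plan says.** Protocol section 14.2, repeated in the SAP under Secondary Objectives, gives the analysis model: "A model of the form $Y(t) = a + b_1 X + b_2 t_4 + b_3 X t_4$ will be used", with two groups and two times (baseline and 4 months). On inference it says that "An unstructured covariance matrix, an identity link function, and robust standard errors will be used", and that the effect is assessed by estimating the size of b3. Section 14.1 states the primary aim but no model. Section 14.2 names the 6MWT as the primary outcome of the GEE, so I read the GEE as covering it.

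The significance level appears only in section 14.4 and its SAP counterpart, as an assumption of the power calculation: "assuming two-sided tests and an alpha level of 0.05". The same section gives the evaluable numbers: "so effective n=94 compared to n=27 including attrition" for the comparison with CAP, and "n=17 in CAP-MP PUSH group vs n=27 in pilot study" for outcomes measured only in CAP-MP.

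Section 14.3 adds inverse-probability weights to the same GEE. Section 15.1.3 says that SAS data sets will be used, but names no procedure or option. Neither document mentions a bias correction, a t or normal reference, or degrees of freedom.

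**The concern.** A sandwich variance relies on having many independent units. With few, the ordinary version is biased low, because residuals are smaller than the errors they stand in for. GEE output then usually refers the estimate to a normal distribution, which ignores the uncertainty in the variance. Both effects shorten the interval and raise the false-positive rate.

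Here the independent units are people, and one group in each comparison is small: 27 in the pilot, and 17 in CAP-MP. At stake is whether the intervals for the 6MWT contrast and the mechanistic contrasts have the coverage that a reader will take them to have. There is a secondary issue: if the plan is silent, the choice of standard error can be made after the results are seen.

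**Working it through.** **Inputs.** Evaluable n of 94 vs 27 and 17 vs 27, two-sided alpha 0.05, 80% power and within-subject correlation r = 0.70 (all section 14.4); the two-by-two GEE (section 14.2). My assumptions: changes are normal with equal SD in both groups, unless stated otherwise.

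**1. The plan's own figure.** For a change-score comparison by normal approximation:

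detectable difference = (1.960 + 0.842) × sqrt(1/n1 + 1/n2) × sqrt(2(1 − r))

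- 94 vs 27: 2.802 × sqrt(0.047675) × sqrt(0.60) = 0.474 SD. The plan states 0.475, so it is reproduced.
- 17 vs 27: 2.802 × sqrt(0.095861) × sqrt(0.60) = 0.672 SD. The plan states 0.62, which is reproduced only with a baseline-adjusted SD of sqrt(1 − r²) (0.6195). That mismatch is a separate matter and is not used below.

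**2. Bias of the ordinary sandwich.** The mean model is saturated, so with complete data b3 is the difference between groups in mean change. Its ordinary sandwich variance is the sum over groups of [(n − 1)/n] × s²/n. I checked this against a fitted GEE on simulated data: the standard error was 0.21287 both ways. With unit SD:

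| | 94 vs 27 | 17 vs 27 |
|---|---|---|
| Target: 1/n1 + 1/n2 | 0.047675 | 0.095861 |
| Expected sandwich: (n1−1)/n1² + (n2−1)/n2² | 0.046190 | 0.091029 |
| Variance ratio | 0.969 | 0.950 |
| SE ratio (square root) | 0.984 | 0.974 |

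**3. Reference distribution.** The Satterthwaite degrees of freedom at equal SD are (1/n1 + 1/n2)² / [(1/n1)²/(n1−1) + (1/n2)²/(n2−1)].

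- 94 vs 27: 42.1 df, critical value 2.018.
- 17 vs 27: 34.2 df, critical value 2.032.

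The width of the uncorrected normal interval relative to the corrected t interval is then:

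- 94 vs 27: 0.984 × 1.960/2.018 = 0.956, about 4% too narrow.
- 17 vs 27: 0.974 × 1.960/2.032 = 0.940, about 6% too narrow.

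**4. Type I error.** As an approximation, it is twice the upper tail of that t distribution beyond 1.960 × SE ratio: 6.0% (94 vs 27) and 6.5% (17 vs 27). Simulation under the null (400,000 runs per scenario, Monte Carlo error about 0.04 points) agrees:

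| Method | 94 vs 27 | 17 vs 27 |
|---|---|---|
| Ordinary sandwich, normal reference | 6.0% | 6.4-6.5% |
| Kauermann-Carroll, Satterthwaite t | 5.0% | 5.0% |
| Kauermann-Carroll, between-subject df (n1 + n2 − 2) | 5.4% | 5.1% |
| Mancl-DeRouen, Satterthwaite t | 4.7% | 4.4% |
| Mancl-DeRouen, between-subject df | 5.1% | 4.6% |

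**5. Sensitivity of the uncorrected test.**

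- Unstructured GEE with 10% of follow-up missing at random (15,000 runs, Monte Carlo error 0.18 points): 6.1% for 105 vs 30 enrolled, 6.3% for 19 vs 30 enrolled.
- Inverse-probability weights estimated from the baseline outcome, 8-11% missing (20,000 runs): about 5.8-6.3% in both comparisons.
- SD 1.5 times larger in the 17-person group (an assumed ratio; the documents give none): about 6.8%. Kauermann-Carroll with Satterthwaite t still gives 5.0%.
- Strongly skewed (lognormal) changes, also assumed: 7.2% for 94 vs 27 and 6.1% for 17 vs 27. The corrected test then gives 6.4% and 4.5%, so at 94 vs 27 most of the excess comes from skewness and the correction does not remove it.

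**The case against.** The strongest objection is that the defect is read from silence. A reader might infer that the plan has chosen uncorrected standard errors and that the 5% level is therefore not delivered. The documents do not support that. They say robust, and Kauermann-Carroll and Mancl-DeRouen standard errors are robust too. They name no reference distribution, and SAS without procedure or options settles nothing. This objection stands, and the finding must be conditional: the specification is incomplete, and its usual default is anti-conservative.

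Second, the size is small. The excess is about 1 point for the primary contrast and 1.5 points for CAP-MP outcomes. The larger figure of 6.8% rests on an SD ratio that appears nowhere in the documents. Under weighting with missingness related to baseline, the CAP-MP comparisons were not consistently worse than the primary one. This also stands, though the inflation did not disappear.

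Third, section 14.2 states no significance rule, and the study is a pilot of 30 people compared with earlier trial participants who were not randomised against them. A correction of 5% in interval width does nothing about that larger uncertainty. A reader might also infer that the sample size of a later definitive trial would be distorted. It would not be by this route: with the same weights, neither b3 nor the outcome SD depends on the choice of standard error.

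What remains is that b3 will be reported with an interval, that the power statement assumes a two-sided 0.05 test, and that the default would miss this level in a known direction at almost no cost to put right.

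**Conclusion.** The point holds as a gap in specification. If the gap is filled by the ordinary sandwich variance with a normal reference, two-sided type I error is about 6.0% for 94 vs 27 and about 6.5% for 17 vs 27, and 95% intervals are about 4% and 6% too narrow. These figures rest on normal changes with equal SD and on the plan's own evaluable numbers. Modest departures (10% missing, estimated weights, unequal SD) leave the uncorrected error at about 6-7%.

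The direction is certain from the algebra; that the plan's analysts would use the uncorrected form is not. Given the size of the excess and the non-randomised pilot design, the priority is low to moderate.

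**What to change.** Add one sentence to Protocol section 14.2 and the same sentence to the SAP: b3 will be tested, and its 95% interval formed, with the Kauermann-Carroll bias-corrected sandwich variance and a t reference with Satterthwaite degrees of freedom, for the 6MWT and all continuous CAP and CAP-MP outcomes.

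Name this one combination and leave no menu. Kauermann-Carroll with between-subject degrees of freedom leaves 5.4% for the primary comparison, and Mancl-DeRouen with Satterthwaite overcorrects to 4.4% for 17 vs 27.

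The cost is intervals about 5% wider for 94 vs 27 (1/0.956 = 1.046) and about 6% wider for 17 vs 27 (1/0.940 = 1.064). The t reference moves the detectable change-score difference from 0.474 to about 0.485 SD and from 0.672 to about 0.69 SD. The point estimate is unchanged. For clearly skewed outcomes the correction is not a full remedy, so the text should not claim that it guarantees the nominal level.
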